8.2 Study Materials

8.2.1 Contact lens

CooperVision will provide the site with an inventory of both study lenses (**LENS A**) and (**LENS B**) to allow participants to be fit with the lens powers available for this study i.e., sphere +4.00D to - 6.00D, in 0.25D steps, in both add powers.

All subjects will be trial fitted and, if suitable, dispensed the first pair of the assigned lens brand assigned per a determined table (Appendix 3). The lenses used in this study are all FDA approved and marketed products. Details of the study contact lenses are shown in Table 1.

Table1: Study lens parameters

Brand	Clariti Monthly Multifocal (LENS A)	Clariti 1-Day Multifocal (LENS B)	
Manufacturer	CooperVision	CooperVision	
Material	somofilcon A	somofilcon A	
FDA Class Group 5		Group 5	
WC %	56%	56%	
Base Curve (mm)	8.6	8.6	
Lens Diameter (mm) 14.1		14.1	
Sphere Power (D) +4.00 to -6.00 (0.25 steps)		+4.00 to -6.00 (0.25 steps)	
Add Power (D) Low, High (see fitting guide)		Low, High (see fitting guide)	
Wearing schedule Daily wear		Daily wear	

8.2.2 Contact Lens care

Since this is a non-dispensing fitting study no contact lens care will be required. However, in the event that the study lenses need to be rinsed during the insertion process, preserved saline solution will be used.

8.2.3 Storage of Study Medications/Treatments

There are no unapproved investigational products used in this study requiring special storage accommodations.

8.2.4 Clinical Supply Inventory

There are no unapproved investigational products used in this study requiring special inventory requirements.

8.2.5 Disposal of Consumables

This study dispenses consumables (lenses) to participants for use during the study. Study lenses worn by participants will be discarded by the principal investigator at the end of the study.

8.2.6 Masking and Control of Study Materials

The contact lenses, (**LENS A**, and **LENS B**), will be masked to the subject only. The lenses will be removed from their blister pack by an assistant and transferred to an unmarked lens case to maintain the participants masked of the study lenses. Participants will then be instructed to remove the lenses from the lens case and insert them onto their eyes. It is not possible for the study investigators to be masked because of the need to follow the specific lens fitting guide during the lens prescription optimization visit.

8.2.7 Ordering and Accountability of Study Materials

The study sponsor will supply the investigators with the study lenses to use during the study.

8.3 Visit Schedule and Procedures

This will be an interventional, subject masked, bilateral, non-dispensing fitting study. Participants will be examined at two different points over the course of one day, V1 (lens dispensing), V2 (15 minutes post lens settling). Participants will wear two different pairs of lenses with **LENS A** fitted first to all participants, followed by **LENS B**. Anterior ocular health examination will be performed at baseline without the use of fluorescein*.

The following outline identifies the two study visits and the general procedures, (Appendix 5), to be conducted at each visit for each day of the study and recorded in the case report forms (Appendix 6):

8.3.1 Visit 1: Baseline / Trial Fit / Lens order

- Explanation of the study.
- Sign informed consent form.
- •
- Insert trial **LENS A**, evaluate the fit and optimize the prescription if needed.
- •
- Order final LENS A.
- Remove LENS A and insert trial LENS B. Evaluate fit and optimize the prescription if needed.
- •
- Order final LENS B.

8.3.2 Visit 2: Lens dispensing (Fit LENS A / Evaluate)

- Subjective assessments

 - Comfort on insertion (0 -10 scale)
- - ____

^{*} Fluorescein will not be used before lens dispensing to prevent potential eye discomfort that could influence subjective comfort ratings after lens fitting and settling. However, fluorescein will be instilled at the last visit upon lens removal.

8.3.3	Visit	3: (Evaluate LENS A)
8.3.4		3: Lens dispensing (Fit LENS B / Evaluate) ubjective assessments
	>	Comfort on insertion (0 -10 scale)
	į	
8.3.5	Visit	4: (Evaluate LENS B / Study Exit)
	֓֡֟֝֟֓֓֓֓֓֓֓֓֓֓֓֓֓֓֓֓֓֓֓֓֓֓֓֓֓֡֓֓֡֓֓֓֡֓֓	

9 Adverse Event Reporting

9.1 Adverse Response Definitions

Adverse Event (AE): An AE refers to any untoward medical occurrence (sign, symptom or disease) in a trial subject that does not necessarily have a causal relationship with the study device. AEs may be classified as 'unanticipated adverse device effects,' 'serious AEs,' 'significant AEs,' or 'non-significant AEs,' as defined below.

Classification	Definition
Serious Adverse Event	Those events that are life-threatening, or result in permanent impairment of a body function, or permanent damage to a body structure or necessitate medical (therapeutic) or surgical intervention to preclude permanent impairment of a body function or permanent damage to a body structure.
Unanticipated Adverse Device Effect	Adverse events in a clinical trial that were not previously identified in the protocol in terms of nature, severity, or degree of incidence. An Unanticipated Serious Adverse Device Effect is an unanticipated adverse event that is serious in nature and caused by or associated with the device and is considered reportable.
Significant Adverse Event	Those non-serious adverse events that occur with contact lens usage that are not sight-threatening but are usually symptomatic and may warrant therapeutic management and /or temporary or permanent discontinuation of contact lens wear.
Non-Significant Adverse Events	Those less severe non-serious adverse events that occur with contact lens usage that are not sight-threatening, may or may not be symptomatic and may warrant palliative management, such as ocular lubricants or temporary interruption of contact lens wear.

AE classification, coding (for reporting to the sponsor) and examples are provided in the following table of Contact LENS Adverse Event Classification and Reporting:

Code	Condition	Potential AE Classification	Reporting
01	Presumed infectious corneal ulcer	SERIOUS	
02	Permanent loss of ≥2 lines of best spectacle corrected visual acuity (BSCVA)	SERIOUS	
03	Corneal injury that results in permanent opacification within central cornea (6mm)	SERIOUS	Notify sponsor as
04	Neovascularization within the central 6mm of cornea	SERIOUS	soon as possible, within 24 hrs; IRB
05	Uveitis or Iritis	SERIOUS	reporting as per
06	Endophthalmitis	SERIOUS	requirements
07	Hyphema	SERIOUS	
08	Hypopyon	SERIOUS	
09	Persistent epithelial defect	SERIOUS	
00	Other serious event	SERIOUS	
11	Peripheral non-infectious ulcer (outside central 6mm)	SIGNIFICANT	
12	Symptomatic corneal infiltrative events	SIGNIFICANT	
13	Superior epithelial arcuate lesions (SEALs) involving epithelial split	SIGNIFICANT	
14	Any temporary loss of ≥2 lines BSCVA for ≥2wks	SIGNIFICANT	
15	Corneal staining ≥ dense coalescent staining up to 2mm in diameter (i.e. moderate staining)	SIGNIFICANT	
16	Corneal neovascularization ≥ 1.0mm to 1.5mm vessel penetration (if 2 Grade change from baseline)	SIGNIFICANT	Notify sponsor as soon as possible,
17	Any sign and/or symptom for which subject is administered therapeutic treatment or which necessitates discontinuation of lens wear for ≥ 2 weeks	SIGNIFICANT	within 5 working days; IRB reporting as per requirements
10	Other significant event	SIGNIFICANT	
21	Conjunctivitis: bacterial, viral, allergic	NON-SIGNIFICANT	
22	Papillary conjunctivitis if ≥ mild scattered papillae/follicles approximately 1mm in diameter (if 2 Grade change from baseline)	NON-SIGNIFICANT	
25	Asymptomatic corneal infiltrative events	NON-SIGNIFICANT	
26	Localized allergic reaction	NON-SIGNIFICANT	
27	Contact dermatitis	NON-SIGNIFICANT	

28	Any sign and/or symptom for which temporary lens discontinuation for > 1 day is recommended	NON-SIGNIFICANT
20	Other non-significant sign and/or symptom	NON-SIGNIFICANT

Normal or adaptive symptoms

Transient symptoms such as end-of-day dryness, LENS Awareness, itching or burning or other discomfort may occur with contact lens wear and may occasionally reduce wearing time. These are not reported as adverse events unless they are unexpected in nature, severity or rate of occurrence.

9.2 Procedures for Adverse Events

Treatment of an adverse event will depend on its nature and severity. Based on the clinical judgment of the investigator the subject may be referred to an ophthalmologist for treatment. The investigator will attempt to determine whether the reaction is related to the test device or a result of other factors.

An Adverse Event Form will be completed for each adverse event. If both eyes are involved, a separate Adverse Event Form will be completed for each eye. Whenever possible, the adverse event will be photo-documented.

Expenses incurred for medical treatment as part of study participation will be paid by the sponsor (bills and prescription receipts kept). The subject must be followed until resolution and a written report completed indicating the subsequent treatment and resolution of the condition.

9.3 Reporting Adverse Events

All potential **Serious and Unanticipated Adverse Device Effects** that are related or possibly related to subject participation in the investigation will be reported to the Principal Investigator and the sponsor within 24 hours of the investigator becoming aware of the event. The Principal Investigator will report the event to the EC/IRB as soon as possible (by fax, mail/delivery, phone, or email), but within 10 business days of becoming aware of the problem. *All fatal or life threatening events will be reported immediately to the IRB*.

Significant and Non-Significant Adverse Events will be reported to the sponsor as soon as possible, but no later than 5 working days after the occurrence.

16

9.4 Discontinuation from the Study

All discontinuations will be fully documented on the appropriate CRF Exit and Adverse Event forms as needed. Participants will be followed until resolution (in most instances) and are free of the ophthalmic insert related complications or other ocular pathology. When possible study lenses involved in an Adverse Event will be returned to the sponsor in a new tightly sealed contact lens case, and labeled with the subject identification and stored in Unisol non-preserved saline.

[figure not shown]
10 Statistical Analysis

[figure not shown]
10.1 Statistical analysis

Summary statistics will be produced, (e.g., mean, standard deviation), by the principal investigator ([name]). Differences between lenses will be compared using Paired t-tests. Paired t-tests /analysis of variance for normal (interval/continuous) data, Wilcoxon's signed ranks test for non-normal (ordinal) data, chi-squares test for nominal data. A Chi-Square test will be used to evaluate lens preference questions. All participants who are evaluated in the study will be used in the analysis. In the event of missing data individual number of points will be excluded in the analysis and not extrapolated from the collected data. The critical alpha level for statistical significance will be set at p \leq 0.05, with adjustment for multiple comparisons.

10.2 Sample size

The sample size was calculated using data of lens comfort at insertion on day 1 collected in a previous study that evaluated the clariti 1day multifocal lens (CooperVision, data on file). Figure 1 shows the sample size determination for a paired t-test, (alpha=0.05), in order to detect a difference Assuming a standard deviation of 2.2, a sample size of 40 completed subjects provides 80% power to detect a difference of 1.0 points on a 0 - 10 scale in subjective comfort ratings at insertion.

Paired t Test

Testing mean paired difference = 0 (versus \neq 0) Calculating power for mean paired difference = difference α = 0.05 Assumed standard deviation of paired differences = 2.2

Results			
Difference Sam	ple Size Targ	et Power A	tual Power
1	40	0.80	0.800497
1 1	40 45	0.80 0.84	0.800497 0.846619

11 Data Quality Assurance

11.1 Study monitoring

A site visit or discussion may be conducted during the course of the study as appropriate. Prior to final data freeze, a close-out visit/discussion may be warranted to check for accuracy and completeness of records. The sponsor or sponsor's representatives will be authorized to gain access to the source documentation for the purposes of monitoring and auditing the study.

11.2 Record keeping

Detailed records of all study visits will be made using the electronic Case Report Forms (CRFs).

11.3 Record retention

Following study completion, data will be available in electronic and/or paper format for audit, sponsor use, or subsequent analysis. The original clinical raw data (including completed CRFs and Informed Consent forms) will be retained according to guidelines set forth in the general work agreement with the site. The Sponsor will be notified and consulted if ever the files are to be destroyed. In the event that this implementation document is indicated for design verification and validation purposes, as indicated on the title page, all original raw data forms and completed CRF's will be forwarded to the sponsor at completion of the final report.

11.4 Data Entry / Data Management

Data will be entered into an electronic spreadsheet. Study staff will only be able to modify the data file via password entry. The investigators will be responsible for the data integrity, and complete data entry for each visit as well as the take home questionnaires. The investigator will send the data collected to the study sponsor within 5 business days after the last subject completes the final visit. A full report will be provided by the investigator at the mutually agreed timeline after the study completion date.

[figure not shown]

11.6 Publication

The investigators will not be permitted to publish or present at scientific meetings results obtained from the clinical study without prior written consent from the sponsor.

13 Appendixes

APPENDIX 1 - STATEMENT OF INFORMED CONSENT

APPENDIX 2 – STUDY TIMELINE

APPENDIX 3 - LENS RANDOMIZATION

APPENDIX 4 – LENS REPLACEMENT LOG

APPENDIX 5 - GRADING & MEASUREMENT SYSTEM

APPENDIX 6 - CRF's / UNSCHEDULED VISIT & ADVERSE EVENT FORM

APPENDIX 1 – STATEMENT OF INFORMED CONSENT

APPENDIX 2- STUDY TIMELINE

TASK	April-2022	May-2022	June-2022	July-2022
Generate study Protocol.	April 12- 16			
Protocol EC submission.	April 18-22			
Protocol EC approval.		May 2		
V1: (BL/trial fit/lens order)		May 3-20		
V2-V4: (Dispense and evaluate both pairs of lenses)		May 30 – J	une 17	
Data analysis			June 20-25	
Study report.				July 4-8

APPENDIX 3 – RANDOMIZATION TABLE

APPENDIX 4- STUDY LENS REPLACEMENT LOG

Date	Investigator Initials	Subject Initials	Visit Just Prior to Lens Replacement	Number of Days Lens was Worn prior to Replacement	Lens Replaced (check one)	Reason
Click here to enter a date.					□ Right □ Left □ Both	
Click here to enter a date.					☐ Right ☐ Left ☐ Both	
Click here to enter a date.					☐ Right ☐ Left ☐ Both	
Click here to enter a date.					□ Right □ Left	
Click here to enter a date.					□ Both □ Right □ Left	
Click here to enter a date.					□ Both □ Right □ Left	
Click here to enter a date.					□ Both □ Right □ Left	
Click here to enter a date.					□ Both□ Right□ Left	
Click here to enter a date.					□ Both□ Right□ Left	
Click here to enter a date.					□ Both□ Right□ Left	
Click here to enter a date.					☐ Both ☐ Right ☐ Left	
Click here to enter a date.					□ Both□ Right□ Left□ Both	
Click here to enter a date.					☐ Right ☐ Left ☐ Both	
Click here to enter a date.					☐ Right ☐ Left ☐ Both	

APPENDIX 5 - GRADING & MEASUREMENT SYSTEM

Variable	Assessment Method	Grading/Measurement System		
Wearing Times				
Average # of days lenses worn in a week	Enter the number of days lenses are worn during the week.	Days per week		
Average Daily Wearing Time	Typical time of day when lenses inserted and removed.	Time of day to nearest half hour		
Average # of hours of wear per day	Enter the number of hours lenses are worn per day.	Hours per day		
Average Comfortable Wearing Time	Typical time of day when subject first experiences LENS Awareness or irritation.	'Does CL comfort deteriorate during wear?' (tick- box). If yes, record time of day to nearest half hour when first aware of lenses		
Typical Removal Time	Typical time of day when subject removes the lens.	Time of day to nearest half hour		
Subjective	Assessments (Questions asked by t	he investigator and recorded)		
Comfort, dryness, handling, lens fit, vision satisfaction.	Assessed by subject on a 0-10 scale.	0-10 scale Comfort: (10= can't feel) Dryness: (10=no dryness) Handling: (10=very easy) Fit stability (10=very stable) * Vision: (10=very satisfied)		
Vision Quality	Assessed by subject on a 0-10 scale.	Vision quality: (10=Excellent vision, totally sharp)		
Night Vision Quality	Assessed by subject on a 0-10 scale.	Vision quality: (10=Excellent vision, totally sharp)		
Vision Stability	Assessed by subject on a 0-10 scale.	Vision stability: (10=perfectly stable, not fluctuating, changing)		
Satisfaction	Subject's assessment of various symptoms on a 4-point Likert scale.	Completely satisfied Somewhat satisfied Somewhat dissatisfied Completely dissatisfied		
Preference	Subject's preference for one of two contact lenses.	Forced choice: Study lenses or Habitual		
Vision				
Distance VA – High contrast	Measured using Snellen or logMAR chart.	Snellen or logMAR visual acuity (VA) to nearest letter.		
Lens Surface assessed using slit lamp				
Front Surface Wettability	Lens surface viewed with a slit lamp, white diffuse light and broad beam under low-medium magnification.	0 – 4 0=poor 4=excellent		

Variable	Assessment Method	Grading/Measurement System		
	Lens surface deposits assessed us	ing the slit-lamp		
Front Surface Deposits	Lens surface deposits viewed with a slit lamp, white diffuse light and broad beam under low-medium magnification.	 Clean, no deposits 5 or less small deposits (<0.1 mm) > 5 deposits of <0.1 mm size or film covering 25-50% of surface Deposits of between 0.1 and 0.5 mm or film covering 50-75% of surface Deposits of 0.5 mm or larger or film covering more than 75% of surface 		
Lens Fit- assessed using slit lamp				
Lens Centration	Lens centration will be recorded by degree and direction in the primary position.	0 Centered - optimal 1 Decentered slightly 2 Substantially decentered (≥0.5mm) If decentered, direction(s) will be recorded as: Superior, Inferior, Nasal, Temporal		
Corneal Coverage	Assessed in primary gaze.	Y Yes, full corneal coverage at all times N No, incomplete corneal coverage		
Post-Blink Movement	Assessed immediately after the blink - lower lid to be depressed only if necessary, for observation.	0 Insufficient, unacceptable movement 1 Minimal, but acceptable movement 2 Optimal movement 3 Moderate, but acceptable movement 4 Excessive, unacceptable movement		
Lens orientation in primary position of gaze	Slit lamp, with 10x magnification. Nasal mislocation is recorded as (+) and temporal as (-)	Mislocation of the axis mark on the lens relative to the 6 o'clock position, zero rotation, measured in degrees.		
Overall stability	Slit lamp, with 10x magnification.	(0–4 scale), where 0=very poor, 4= excellent		
Rotational recovery in degrees after 60 seconds	Slit lamp, with 10x magnification.	LENS Ability to return to its original position measured 60 seconds after manually rotating the lens 45° degrees temporally. Rotational recovery (RR) is assessed by manually rotating the lens 45° temporally from the primary gaze orientation (PGO) and allowing one minute (60 seconds) for the lens to recover. The absolute difference between the position of the lens following the recovery period and the PGO is taken as the measure of interest.		
Overall Fit Acceptance	Assessed by the Investigator based on lens fit alone (i.e., not comfort or vision).	0 Should not be worn 1 Borderline but unacceptable 2 Min. acceptable, early review 3 Not perfect but OK to dispense 4 Perfect		

Variable	Assessment Method	Grading/Measurement System		
Biomicroscopy				
Limbal & Bulbar Hyperemia	Assessed using slit lamp with white light, low-medium magnification. (Use Brien Holden Vision Institute grading scales for reference) ½ grades recorded.	0 NONE: No injection present 1 VERY SLIGHT 2 SLIGHT 3 MODERATE 4 SEVERE		
Lower palpebral hyperemia	Assessed using slit lamp with white light, low-medium magnification. (Use Brien Holden Vision Institute grading scales for reference) ½ grades recorded.	0 NONE: No injection present 1 VERY SLIGHT 2 SLIGHT 3 MODERATE 4 SEVERE		
Corneal Infiltrates	Assessed using slit lamp with diffuse white light, low-medium magnification.	 NONE: No infiltrates TRACE: One faint peripheral infiltrate that does not stain. MILD: A few mild infiltrates MODERATE: Multiple dense infiltrates SEVERE: Marked infiltrates with overlying staining. 		
Other Slit Lamp Findings	This section is intended to capture less commonly observed clinical entities such as conjunctival infection, EKC, corneal ulcers, LENS Adhesions, and recurrent erosions. The complication should be identified, described and graded by severity using the 0-4 scale.	0 None 1 Trace 2 Mild 3 Moderate 4 Severe		

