Soft multifocal contact lenses, (MFCLs), are a great option for new and established presbyopes, offering good vision performance with the added benefit of improved cosmesis and convenience compared to spectacles, and provide them the flexibility to change-up their vision correction. CL manufacturers are continually innovating in this area, with the increased availability of soft MFCLs with novel designs in a range of replacement frequencies from daily disposable to monthly replacement, and different materials including silicone hydrogels.

Therefore, CooperVision is interested in comparing the short-term clinical performance and subjective acceptance of Clariti Monthly Multifocal, (**LENS A**), to the Clariti 1-Day Multifocal, (**LENS B**), silicone hydrogel contact lenses. A non-dispensing fitting study is proposed to evaluate the short-term clinical performance of these lenses.

2 Study Objective

The aim of this non-dispensing fitting study is to evaluate the short term lens fit, vision performance and patient subjective experiences of the Clariti Monthly Multifocal when compared to the Clariti 1-Day Multifocal after 15 minutes of daily wear.

The primary outcome variable is:

Subjective comfort ratings on insertion (assessed by subjects)

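### Minor, cheap improvement: let the masked participant complete the 0-10 comfort and handling ratings in writing before any discussion with the unmasked investigator

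*Combined protocol and SAP*

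**What the plan says.** **Outcome.** Section 2 gives the primary outcome as "Subjective comfort ratings on insertion (assessed by subjects". Sections 8.3.2 and 8.3.4 place it at dispensing of each lens pair: "Comfort on insertion (0 -10 scale". The synopsis also lists subjective handling, at insertion and removal, under Primary Endpoint.

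**Collection.** The subjective block of Appendix 5 covers comfort, dryness, handling, fit and vision. Its heading describes questions asked by the "investigator and recorded". The entry for these items reads "Assessed by subject on a 0-10 scale". Only the upper end of each scale is worded, for example "Dryness: (10=no dryness) Handling: (10=very easy".

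**Masking.** Section 8.2.6 masks the lenses to the participant only. An assistant moves them to an unmarked case. For the other side it states: "It is not possible for the study investigators to be masked". The reason given is the need to follow the fitting guide when the prescription is optimised.

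**Order.** Section 8.3 has LENS A "fitted first to all participants, followed by" LENS B. Section 8.2.1 instead has the first pair assigned from a table in Appendix 3, which is titled as a randomization table.

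**Recording.** Section 11.2 specifies electronic CRFs. Section 11.4 makes the investigators responsible for complete data entry at each visit. No visible passage says who writes down a spoken score.

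**The concern.** Participant masking is the only masking in this study, and it protects the participant's judgement. If the person asking for the score knows which lens is in the eye, wording, tone, follow-up questions or transcription could differ between lenses. That is a recognised interviewer-bias route, and here it runs through the primary outcome.

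The exposure looks avoidable on the plan's own reasoning. Following a fitting guide explains why the fitter cannot be masked. It does not explain why someone who knows the lens has to ask the comfort question.

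At stake is whether an observed difference in comfort or handling reflects the lenses alone. The visible text has no scripted wording, no masked interviewer and no self-completion step for the insertion rating.

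**Working it through.** **Inputs (section 10.2).** Paired t-test, two-sided alpha 0.05, SD of paired differences 2.2, n = 40, difference 1.0 on the 0-10 scale.

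**1. Reproduce the plan's figure.** Noncentrality = (1.0/2.2) × √40 = 2.875, with 39 degrees of freedom. The noncentral t distribution gives power 0.8005. The plan states 0.800497, so it reproduces.

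**2. Standard error of the mean difference.** 2.2/√40 = 0.348 points.

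**3. Isolated recording errors.** One participant's score wrong by 1 point moves the mean by 1/40 = 0.025 points. 0.025/0.348 = 7.2% of the standard error. To move the mean by one standard error takes 0.348/0.025 = 13.9, so 14 of 40 participants, each off by 1 point in the same direction.

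**4. A consistent shift.** The documents give no figure for this, so the shifts below are assumptions that show a range. They are not estimates. The SD is held at 2.2. The second column is the assumed shift divided by 0.025. The last column assumes that the shift works against a true difference of 1.0.

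| Assumed shift in mean A-B difference | Equivalent: participants off by 1 point, same direction | Rejection rate if no true difference | Power |
|---|---|---|---|
| 0 | 0 | 5.0% | 80.0% |
| 0.1 | 4 | 5.9% | 71.3% |
| 0.25 | 10 | 10.8% | 55.7% |
| 0.5 | 20 | 28.9% | 28.9% |

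The table shows what any systematic shift of that size would do, whatever its cause. It is not evidence that this one exists.

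**5. Scope.** Comfort on insertion: 40 participants × 2 lens pairs = 80 ratings. Handling adds more, but its timing is not visible. If the two 15-minute evaluations also carry 0-10 items (an assumption, because those lists are partly blank), there are 40 × 4 = 160 rating occasions.

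**The case against.** The strongest reply is that this is a preference and not a defect. An investigator who asks a masked participant for a number is consistent with sections 2 and 8.2.6 and with Appendix 5. That stands: there is no contradiction and no numerical error here. The point survives only as a better way to collect the same data at small cost.

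The second reply is that the evidence is thin. The Appendix 6 CRFs are not shown and the visit lists are partly blank. Appendix 5 also carries items that do not fit a 15-minute comparison of two study lenses: a preference item worded "Forced choice: Study lenses or Habitual", weekly wearing times, night vision, and rotational recovery for lenses with no listed cylinder. Its heading may be template text. This also stands, and it limits confidence. Even so, if the CRF is self-completed, the heading misdescribes how the primary outcome is collected and should be corrected. The take-home questionnaires in section 11.4 do not settle the matter, since nothing visible ties them to a rating made at insertion in the clinic.

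Third, no directional motive is apparent. Both lenses are the sponsor's, their listed material and parameters match, and the hypothesis is two-sided. That is fair, and it is why no direction is claimed.

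Three stronger readings are tempting, and the documents do not support them:

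- A reader might infer that the asker has to explain the lower end of each scale aloud. The unseen CRF may print it, and a scale whose 10 means the lens cannot be felt already has a clear direction.
- A reader might infer that the investigator writes the score down. The heading says the answers are recorded, without saying by whom.
- A reader might infer from section 8.3 that the asker knows the lens because the order is fixed. Sections 8.2.1 and Appendix 3 leave the order unsettled. The point does not need it, because section 8.2.6 leaves the investigator unmasked in either case.

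**Conclusion.** The point holds as a minor, inexpensive improvement. On the visible text, someone unmasked to the lens asks for the primary comfort rating and for handling. The rating remains the masked participant's, so the risk is confined to prompting or transcription that differs by lens. Its size and direction are unknown. Isolated slips are negligible, and only a consistent shift would matter.

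It would be wrong to conclude that the comfort comparison is biased, or that participant masking fails; nothing visible shows either. Nor should self-completion be presented as removing interviewer influence, because the unmasked investigator still fits both lenses.

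The conclusion rests on the Appendix 5 heading describing actual conduct, which the unseen CRFs could overturn. Confidence is medium.

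**What to change.** Replace the Appendix 5 heading for the subjective block with wording such as: *Completed by the participant before any discussion with the investigator, who checks for completeness only.* Make the matching CRF pages agree for all 0-10 items, handling included. Word both ends of each scale in a one-line written instruction. State whether the participant uses a screen, or a paper sheet that is kept as source and then entered into the electronic CRF. If the CRF is already self-completed, correct the heading only.

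**Cost.** At least 80 short sheets or screens for comfort on insertion, and up to 160 under the assumption above. No live explanation is available while an item is being scored, which the written instruction is meant to cover. Paper adds a data-entry step. Visits, analysis, n = 40 and power of 80% are unchanged.

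**What it leaves open.** If LENS A always comes first, lens and order are confounded, and a change of form does nothing about that. Section 8.3 must be reconciled with section 8.2.1 and Appendix 3 separately.
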